7.2 Recruitment and screening

(ClinO, Art 25, Appendix 3, 1.4 & 1.6; AGEK 5.1; SPIRIT #15)

At Sonova AG Headquarters, a subject database is existing which is currently containing approx. 1000 hearing impaired subjects (various degrees of hearing loss) from circumjacent cantons. Furthermore, this database is containing hearing impaired employees from Sonova AG (internal subjects). The database is permanently extended (study independently) with new subjects recruited via different paths and screened by qualified Audiologists employed at Sonova AG:

- Phonak homepage (status 22.11.2019): <https://www.phonak.com/ch/de/hoerverlust/feldstudie-anmeldung.html>
- Flyer Phonak Feldstudien (see attachment: 4b1_Flyer_Phonak_Feldstudien.pdf)
- Campaign "Probanden werben Probanden" (see attachment: 4b2_Kampagne_Probanden_werben_Probanden.pdf)
- Advertisement in magazine Decibel (see attachment: 4b3_Inserat_Decibel.pdf)
- Links at homepages from organization of hearing impaireds, e.g.:
 - o ProAudito (status 19.05.2015): http://www.proaudito-zuerich.ch/fileadmin/customer/Medien/Home_und_Aktuell/pdf/Inserat_Phonak_sucht_Probanden.pdf
 - o Audiopädagogik.ch (status 19.05.2015): <http://www.audiopädagogik.ch/phonak-sucht-probanden-ab-sofort/>

After the study approval by the CEC and after a subsequent successful Initiation Visit undertaken by the monitor, the subject recruiting by contacting potential candidates can be started. At this initial contact, the time expenditure and the availability period will be discussed in advance. In case of a positive reply, the participant information as well as the informed consent form is sent to the potential study participant by post or email one week prior to the screening appointment, at least, and the subject is invited via telephone or email for an assessment of his hearing at Phonak HQ. The audiological history of a subject and a pure tone audiogram as well as a speech audiogram is recorded, the inclusion and exclusion criteria are requested and open questions concerning the study itself, the participant information and the informed consent form are replied before the decision about a study participation is made and the signed document is collected by the investigator. If a participant quotes hearing a tinnitus, a Tinnitus Pitch and Loudness Matching is executed to determine its frequency and intensity (section 5.1, table 4).

Internal subjects are personally contacted or via email to request their availability and interest in pre-study participation. The screening process is the same as for the external participants. The internal subjects participate on a voluntary basis during their regular working time and contribute to an investigational benefit for the company. In case of any non-attendances of the study, no employment consequences will occur.

All the selected participants will be listed and encoded in a password locked file. Only the study personal and the monitor have access to this file. For all study related appointments at Sonova AG, the participants receive an expense allowance of 25 CHF/hour during the lab trials, of 12.50 CHF per questionnaire (p/eCRF) which is filled in during the home trials (assumed duration of 30 min) and a train ticket (2nd class) from their home address to Sonova AG, [name], by the end of the study.

Please note that from the 6th July 2015 on, the Sonova AG is the family brand as well as the employer and the Phonak AG is the main brand of Sonova's different brands. The Validation Team works for the brand Phonak AG and, therefore, evaluates Phonak Hearing Systems. For this reason, both brands Sonova AG and Phonak AG have the same address and can both officially be used printed on the recruiting material.

7.3 Assignment to study groups

(AGEK 5; SPIRIT #16)

The assignment of the participants is done by chance. The first participants who state their participation and fulfil the inclusion criteria are picked.

7.4 Criteria for withdrawal / discontinuation of participants

(ClinO, Art 9; ICH/E6 6.5.3; SPIRIT #21b)

Subject withdrawal criteria (i.e., terminating investigational product treatment/trial treatment) and procedures specifying: a) When and how to withdraw subjects from the trial/ investigational product treatment. c) Whether and how subjects are to be replaced.

If a subject will be withdrawn (e. g. withdrawal of informed consent, non-compliance, disease progression, safety etc. or study or routine procedure must be stopped, e. g. due to safety concerns), a final assessment of the ear and ear canal will be carried out and all products as well as all study material (e.g. pCRFs) that had been used have to be returned by the participant to the study site. The participants participate on a voluntary basis and can abort the participation on the study at any point of the study. The withdrawn participant will be replaced by another voluntary employee, if needed. The measurement results of the withdrawn participants will be excluded of the evaluation if the results are not complete to be included in the analysis. A new participant has to pass each study trial from the beginning.

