In total, a maximum of 210 adult subjects will participate per year. If necessary, there will be a pre-study with a maximum of five internal (normal hearing or hearing impaired) subjects before the main study to prove the actual study design. A pre-study will be considered if there are adjustments away from the normal audiological standard regarding the method, setup, subject group etc. If a pre-study is necessary will be decided by the principal investigator. Then, according to experience, 6 clinical trials (main studies) with a maximum of 30 subjects per study each of two months duration, are conducted for a quality control of the Phonak Hearing Systems. Typically, each participant gets a series of weekly appointments of 1.5 to 2 hours (lab trials), respectively, including the fitting procedure of the hearing system as well as the objective tests. Between the weekly appointments, the home trials take place so that the subjects can test the devices in their daily life in accordance to some questionnaires either pCRF or eCRF. In dependence on the form factor of an investigational product, which provide different gain levels, participants with appropriate hearing losses ranging from mild, moderate, severe to profound need to be recruited. Testing takes place in one of the three double-walled sound-attenuating booths (Validation Room 1, 2 and 3, see section 9.2.1).

Despite of the well-defined study protocol, some limitations of the study design are inherent. For example, it is not possible to blind the investigational product during the home trial. Especially the housing/naming of competitor devices are revealing their identity. During the lab trials, the participants are fully blinded. An additional limitation of the study design are software updates during the study for both the fitting software and the hearing systems. As soon as quality problems occur, such as acoustic feedback problems or artefacts, for example, a device deficiency form is filled in and the devices get revised leading to different firmware versions across the study which need to be considered during the data analysis.

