7.1 Eligibility criteria

(ClinO, Art 25d5; ICH/E6 6.5.1&6.5.2; AGEK 5.2&5.3; SPIRIT #10)

ICH: Subject inclusion and exclusion criteria.

Only adult subjects will participate. In the pre-study normal hearing persons as well as hearing impaired persons will participate whereas in the main study merely hearing impaired subjects will be involved.

Participants fulfilling all of the following inclusion criteria are eligible for the study:

- Adult (minimum age: 18 years) hearing impaired persons both with and without (experience with) hearing aids
- Good written and spoken (Swiss) German language skills
- Healthy outer ear (without previous surgical procedures)
- Ability to fill in a questionnaire (p/eCRF) conscientiously
- Informed Consent as documented by signature

The presence of any one of the following exclusion criteria will lead to exclusion of the participant:

- Contraindications to the MD in this study, e.g. known hypersensitivity or allergy to the investigational product
- Limited mobility and not in the position to attend weekly appointments
- Limited ability to describe listening impressions/experiences and the use of the hearing aid
- Inability to produce a reliable hearing test result

- Massively limited dexterity
- Known psychological problems
- Central hearing disorders

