8.5 Data Collection and Follow-up for withdrawn participants

(ICH/E6 6.5.3; AGEK 9.2; SPIRIT #18b)

ICH:b) The type and timing of the data to be collected for withdrawn subjects. d) The follow-up for subjects withdrawn from investigational product treatment/trial treatment.

The subjects participate on a voluntary basis and can abort the participation on the study at any point of the study. The withdrawn participant will be replaced by another voluntary employee. The measurement results of the withdrawn participants will be included to the evaluation if data are complete for the appropriate trial. The new participant has to pass each study trial from the beginning.

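### Sections 7.4 and 8.5 name employees as the only replacements for withdrawn participants and do not limit this to the pre-study, so hearing-impaired sponsor staff could enter main-study ratings

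*Combined protocol and SAP*

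**What the plan says.** The replacement rule appears twice in the combined protocol and SAP. Section 7.4: "The withdrawn participant will be replaced by another voluntary employee, if needed". Section 8.5: "The withdrawn participant will be replaced by another voluntary employee", with no condition attached. Both sections are general and neither mentions the pre-study. In both, the new participant starts from the beginning.

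Elsewhere employees belong to the pre-study. Section 6.1: "there will be a pre-study with a maximum of five internal (normal hearing or hearing impaired) subjects before the main study". Section 7.2: "Internal subjects are personally contacted or via email to request their availability and interest in pre-study participation". The same section says that they take part "during their regular working time and contribute to an investigational benefit for the company", and that they are screened in the same way as external participants.

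On hearing status, section 7.1 says that "in the main study merely hearing impaired subjects will be involved", and its first inclusion criterion is "Adult (minimum age: 18 years) hearing impaired persons both with and without (experience with) hearing aids". It contains no criterion on employment by the sponsor. Section 7.2 describes a database of approx. 1000 hearing-impaired subjects and adds that it also holds hearing-impaired employees.

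**The concern.** The main study asks outside hearing-aid users and candidates to judge the sponsor's new devices, and to compare them with earlier models and competitor products. Many of the outcomes in Table 4 and section 9.2.1 are opinions: sound quality, preference, handling and home questionnaires. Sections 6.1 and 6.2.2 concede that the product cannot be fully masked during the home trial.

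If the replacement rule is applied in a main study, an outside rater who leaves is succeeded by someone employed by the manufacturer of the test device. Under sections 7.4 and 11.5 the leaver's incomplete data are dropped, while the employee's complete record is kept. Section 11.4.1 analyses all participants together and forms subgroups by hearing loss and experience, so nothing in the planned analysis would show that an employee was among the raters. Section 13 allows the results to support product claims, which makes the make-up of the comparison sample matter outside the company as well.

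**Working it through.** No stated figure has to be reproduced. The check is a comparison of sections, followed by arithmetic for scale.

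**Step 1: does the rule reach the main study?** Sections 7.4 and 8.5 cover withdrawal for the whole study. Sections 6.1 and 7.2 describe internal subjects as the pre-study group, and section 9.1 keeps pre-study participants out of the main study. No section gives main-study replacements a different source. On its wording, the rule reaches the main study.

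**Step 2: who could enter?** Section 7.1 admits only hearing-impaired persons to the main study, and nothing in 7.4 or 8.5 exempts replacements from it. It does not exclude employees, and the database in 7.2 includes hearing-impaired ones. So the rule can be carried out, with hearing-impaired employees only.

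**Step 3: share of a group.** One replacement is 1/n of the group. Section 11.2 gives benchmark groups of 10 or 15, a usual study size of 20, and up to 30.

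- n = 10: 1/10 = 10%
- n = 15: 1/15 = 6.7%
- n = 20: 1/20 = 5%
- n = 30: 1/30 = 3.3%

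**Step 4: how often?** The documents give no withdrawal rate. I assume d = 5%, 10% or 20%, independent withdrawals, and each one replaced by an employee. Expected replacements are n × d. The chance of at least one is 1 − (1 − d)^n. For n = 10 and d = 10%, that is 1 − 0.9^10 = 65%.

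| n | Expected replacements (5 / 10 / 20%) | Chance of at least one (5 / 10 / 20%) |
|---|---|---|
| 10 | 0.5 / 1 / 2 | 40% / 65% / 89% |
| 15 | 0.75 / 1.5 / 3 | 54% / 79% / 96% |
| 20 | 1 / 2 / 4 | 64% / 88% / 99% |
| 30 | 1.5 / 3 / 6 | 79% / 96% / over 99% |

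**Step 5: effect on a mean.** With r replacements in a group of n, and an employee-minus-outsider difference of b points, the group mean moves by (r/n) × b. Both r and b are assumptions.

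- r = 1, n = 15, b = 1: 1/15 × 1 = 0.07 points
- r = 2, n = 10, b = 1: 2/10 × 1 = 0.2 points
- r = 2, n = 10, b = 2: 2/10 × 2 = 0.4 points

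The rating scales have no stated range, so these shifts cannot be called large or small. In the cross-over of section 6.1 each person rates both devices. A general tendency to rate high or low then cancels, and b has to be read as a preference specific to one device.

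**Step 6: are external replacements available?** The main studies need at most 6 × 30 = 180 subjects a year, against approx. 1000 in the database. Section 6.2 requires a break of at least six months between studies, and not everyone will have the hearing loss that a given device calls for. The margin is still wide.

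**The case against.** The strongest reply is that this is a drafting slip. The word *another* presupposes that the person leaving is also an employee, which fits only the pre-study, so pre-study wording has probably been carried into two general sections. I accept that as the likeliest history, and the documents do not support reading the rule as a deliberate choice. But it remains the only replacement rule in the protocol. Section 2.3 allows no protocol change without prior sponsor and ethics committee approval, so a team that recruits an outside replacement for a main study departs from the text of 8.5.

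A reader might infer more than the documents support, in three ways:

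- **Normal-hearing raters in the main study.** Sections 7.1 and 7.2 rule this out: hearing impairment is required, and employees are screened like everyone else.
- **Automatic replacement of every withdrawal.** Section 8.5 reads that way, but section 7.4 makes replacement conditional on need. The two disagree.
- **A proven bias in the sponsor's favour.** No section gives an employee effect. For the zero-defect objective an employee might report more faults, since section 6.1 has quality problems documented and the devices revised. It is equally unsupported that people leave because they dislike a device; the examples in 7.4 are withdrawn consent, non-compliance, disease progression and safety.

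It is also fair to say that exposure is limited. Section 6.1 describes participants as fully blinded in the lab, many measures in Table 4 are objective, and section 11.1 says that no specific hypothesis is tested. These points narrow the concern to benchmark and home-trial ratings. They do not remove it.

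**Conclusion.** The point holds as an inconsistency that carries a risk of bias. The replacement rule in 7.4 and 8.5 conflicts with the use of internal subjects in 6.1 and 7.2, and the two statements of the rule differ on whether replacement is conditional. Applied literally, it lets sponsor staff with hearing loss into main-study subjective ratings and competitor comparisons.

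The only size that follows from the documents is the share: 10% of a group of 10, or 6.7% of a group of 15, per replacement. The frequency of replacement and any shift in ratings rest on assumed values. A lean towards the sponsor's product is a reasonable worry for the benchmark and the home trial, where the product may be recognised, but neither its direction nor its amount is established.

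**What to change.** 1. Put the same text in 7.4 and 8.5, for example: 'Employees may replace only pre-study participants. In the main study a withdrawn participant is replaced, if needed, by an eligible external hearing-impaired subject from the database who meets the criteria in section 7.1.'
2. Add to 7.1 or 7.2 that internal subjects are not enrolled in the main study. Changing the replacement rule alone would leave first enrolment open, because no current criterion excludes the hearing-impaired employees in the database.
3. If an employee has already entered a main study, report its zero-defect and benchmark results with and without that person.

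The cost is a few sentences in an amendment, and possibly one extra run of an analysis. The number of participants does not change. The small downside is that an external replacement may take slightly longer to schedule than a colleague on site.

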8. STUDY INTERVENTION

(SPIRIT #11)

8.1 Identity of Investigational Products (treatment / medical device)

(ICH/E6 6.2.1, 6.4.2, 6.4.4; AGEK Checklist 2, item 3)

ICH: A description of the trial treatment(s) and the dosage and dosage regimen of the investigational product(s).

This section describes all trial treatments for each arm of the study.

8.1.1 Experimental Intervention (treatment / medical device)

ICH: Name and description of the investigational product(s).

All investigational devices are CE marked and based on the latest Phonak Hearing System portfolio (all form factors and performance levels, see http://www.phonak.com/ch/b2c/de/products/hearing_instruments.html, status 20.05.2015). This includes MD of risk category IIA: Phonak Hearing Systems comprising hearing aids, acoustic coupling (receiver and earpiece), fitting software and of risk category I: Wireless accessories (transmitters and receivers). The application is done according to the specialised information.

8.1.2 Control Intervention (standard/routine/comparator treatment / medical device)

ICH: Name and description of the investigational product(s).

Previous outstanding Phonak Hearing Systems as well as equivalent strong competitor devices.

8.1.3 Packaging, Labelling and Supply (re-supply)

ICH: Also include a description of the dosage form, packaging, and labelling of the investigational product(s).

N/A

8.1.4 Storage Conditions

All MD and MD supplies have to be stored according to standard procedures as mentioned in the

manufacturer directions. The hearing aids will be stored in their hearing aid cases (dry and dust-free). There are no special environmental conditions necessary for storage.

8.2 Administration of experimental and control interventions

(ICH/E6 6.4.4)

8.2.1 Experimental Intervention

ICH: Description of and justification of the treatment(s) to be administered, including the name(s) of all the product(s), the dose(s), the dosing schedule(s), the route/mode(s) of administration, and the treatment period(s), including the follow-up period(s) for subjects for each investigational product treatment/trial treatment group/arm of the trial.

Please find the description of route, dose, study procedure and the utilization period of the investigational medical devices in chapter 3.5, 5, 6.1 and in the section STUDY SCHEDULE.

8.2.2 Control Intervention

ICH: Description of and justification of the treatment(s) to be administered, including the name(s) of all the product(s), the dose(s), the dosing schedule(s), the route/mode(s) of administration, and the treatment period(s), including the follow-up period(s) for subjects for each investigational product treatment/trial treatment group/arm of the trial.

Same as in 8.2.1.

8.3 Dose / Device modifications

(SPIRIT #11b)

N/A

8.4 Compliance with study intervention

(ICH/E6 6.6.3; AGEK Checklist 2, item 2; SPIRIT #11c)

ICH: Procedures for monitoring subject compliance.

N/A

8.5 Data Collection and Follow-up for withdrawn participants

(ICH/E6 6.5.3; AGEK 9.2; SPIRIT #18b)

ICH:b) The type and timing of the data to be collected for withdrawn subjects. d) The follow-up for subjects withdrawn from investigational product treatment/trial treatment.

The subjects participate on a voluntary basis and can abort the participation on the study at any point of the study. The withdrawn participant will be replaced by another voluntary employee. The measurement results of the withdrawn participants will be included to the evaluation if data are complete for the appropriate trial. The new participant has to pass each study trial from the beginning.

8.6 Trial specific preventive measures

(ICH/E6 6.6.2; AGEK 9; SPIRIT #11d)

ICH: Medication(s)/treatment(s) permitted (including rescue medication) and not permitted before and/or during the trial.

To avoid discomfort through too loud output levels of the hearing aids which could harm the subjects ear, the uncomfortable level (UCL) will be measured within the pure tone audiogram during the screening appointment. The UCL will be used for the fitting of the hearing aids to ensure a comfortable maximum power output.

After fitting the hearing aids to the individual hearing loss of the subject, the subjective acceptance of loud input signals will be tested (tolerance test) to ensure that the individual maximum power output (based on the UCL measurement) of the hearing aids is guaranteed and accepted by the subject.

8.7 Concomitant Interventions (treatments)

(ICH/E6 6.6.2; AGEK 9; SPIRIT #11d)

ICH: Medication(s)/treatment(s) permitted (including rescue medication) and not permitted before and/or during the trial.

N/A

8.8 Study Drug / Medical Device Accountability

(ICH/E6 6.4.7; AGEK Checklist 2, item 1; SPIRIT 11c)

ICH: Accountability procedures for the investigational product(s), including the placebo(s) and comparator(s), if any.

The accountability for the MD is ascribed to both the according Project Leader (PL) of the Research & Development Department and the Product Manager of the Marketing Department in the Sonova AG, Stäfa. The PL and the PM are also the persons addressed in case of any device deficiencies (receivers of the device deficiency form).

8.9 Return or Destruction of Study Drug / Medical Device

(AGEK Checklist 2, item 1; SPIRIT 11c)

At the end of the study during the final appointment, all study devices will be returned to the according PI.

9. STUDY ASSESSMENTS

(ICH/E6 6.7, 6.8; AGEK 6, 7; SPIRIT #18a)

This section includes a description of the procedures, measurements, collections and storage of samples taken.

9.1 Study flow chart(s) / table of study procedures and assessments

A study maybe a combination of a pre-study, if necessary, and a main study where of both include objective and subjective measurements. A maximum of 5 subjects will take part in the pre-study and a maximum of 30 will take part in the main study which does not include the pre-study participants. Please note the following tables repeat those of section STUDY SCHEDULE.

Study Period	Screening	Pre-study appointments		Follow-up (final appointment)
Visit Number	1	2	3	4
Time [hrs]	1.5	2	2	2
Audiological History	x			
Physical Examination of Ear and Ear Canal	x	x	x	x
Audiogram	x			x
Tinnitus Matching	x			x
Check In- /Exclusion Criteria	x			
Decision Subject Participation	x			
Subject Information and Informed Consent	x			
Encoded Subject ID	x			
eCRF Screening	x			
eCRF Audiometry	x			x

Randomisation	x			
Hearing System Fitting	x	x	x	
Objective and Subjective Measurements		x	x	(x)
eCRF Objective and Subjective Measurements		x	x	(x)
Introduction to Handling		x	x	
Scheduling Next Visit		x	x	
eCRF Final Appointment				x
Capture of Adverse Events and Device Deficiencies	x	x	x	x

Table 1a: Pre-study: N = max 5

Study Period	Screening	Study appointments										Final Appointment
		1	2	3	4	5	6	7	8	9	10	
Visit Number	1.5	2	2	2	2	2	2	2	2	2	2	2
Time [hrs]	1.5	2	2	2	2	2	2	2	2	2	2	2
Audiological History	x											
Physical Examination of Ear and Ear Canal	x	x	x	x	x	x	x	x	x	x	x	
Audiogram	x											x
Tinnitus Matching	x											x
Check In-/Exclusion Criteria	x											
Decision Subject Participation	x											
Subject Information and Informed Consent	x											
Encoded Subject ID	x											
eCRF Screening	x											
eCRF Audiometry	x											x
Randomisation	x											
Hearing System Fitting	x											
Objective and Subjective Measurements		x	x	x	x	x	x	x	x	x	x	(x)

eCRF Objective and Subjective Measurements		x	x	x	x	x	x	x	x	x	X	(x)
Introduction to Handling		x	x	x	x	x	x	x	x	x	x	
Scheduling Next Visit	x	x	x	x	x	x	x	x	x	x	x	
eCRF Final Appointment												x
Capture of Adverse Events and Device Deficiencies	x	x	x	x	x	x	x	x	x	x	x	x

Table 1b: Main study: N = max 30 (no pre-study subjects)

